5.2 Exclusion Criteria

Participants who meet any of the following criteria during Screening will not be eligible to participate in the study:

1. History of treatment with any PTH analog (i.e., PTH 1-84, PTH 1-34, TransCon PTH, etc.) within the previous 3 months
2. History of prior treatment with encaleret
3. History of hypocalcemic seizure within the past 3 months

4. Blood 25-OH Vitamin D level <25 or >60 ng/mL
 - a. If subject has a blood 25-OH Vitamin D level < 25 ng/mL at the screening visit, they will be prescribed cholecalciferol or ergocalciferol supplementation. Once the 25-OH Vitamin D level is \geq 25 ng/mL, the subject will be eligible to continue to the treatment phase of the study.
 - b. If a subject has a blood 25-OH Vitamin D level >60 ng/mL at the screening visit, their vitamin D supplementation will be adjusted. Once the 25-OH Vitamin D level is \leq 60 ng/mL, the subject will be eligible to continue to the treatment phase of the study.
5. Participants with hemoglobin (Hgb) lower than the lower limit of normal.
 - a. If subject has a low Hgb at the screening visit due to iron, B12, or folate deficiency, they will be prescribed supplementation. Once the Hgb level within the normal range, the subject will be eligible to continue to the treatment phase of the study.
6. Abnormal laboratory values which in the opinion of the investigator, would make the subject not suitable for participation in the study
7. Estimated glomerular filtration rate (eGFR) < 50 mL/minute/1.73 m² using CKD-EPI.
8. Insufficient hepatic function defined as one of the following:
 - Total Bilirubin > 1.5 x ULN OR
 - Aspartate transaminase (AST) > 2x ULN OR
 - Alanine transaminase (ALT) > 2x ULN
9. 12-lead resting electrocardiogram (ECG) with clinically significant abnormalities. Participants with screening QTcF (using the Frederica equation) > 450 milliseconds (ms) will not be eligible for the treatment phase of the study.
 - If a participant has a prolonged QTcF during screening due to a reversible cause of long QT (for example hypocalcemia or QT-prolonging medications), the subject may be eligible for the treatment phase of the study if the reversible cause can be addressed, and repeat ECG shows QTcF \leq 450 milliseconds.
10. Clinically significant cardiac disease including any of the following:
 - Congestive heart failure requiring treatment (NY Heart Association grade \geq 2)
 - History of clinically significant cardiac arrhythmias including ventricular arrhythmias, atrial fibrillation, or conduction abnormalities
 - History of unstable angina pectoris or acute myocardial infarction
11. Participants with positive hepatitis B surface antigen (HBsAg) or Hepatitis A immunoglobulin M (IgM) at the Screening Visit. Participants who are in complete remission from Hepatitis C as evidence by sensitive assay \geq 12 weeks after completion of HCV therapy are allowed to participate in the study. Participants with human immunodeficiency virus (HIV) infection on a stable dose of anti-retroviral therapy who have an undetectable viral load are allowed to participate in the study.

12. Pregnant or nursing (lactating) women, where pregnancy is defined as the state of a female after conception and until the termination of gestation, confirmed by a positive serum hCG laboratory test
13. Clinically significant abnormalities in thyroid function tests. This does not include participants with non-clinically significant or treated thyroid diseases (e.g. subclinical hypothyroidism, hypothyroidism on treatment, etc). Participants on TSH-suppression therapy for thyroid cancer are allowed to participate in this study regardless of TSH level.
14. Women of child-bearing potential, defined as all women physiologically capable of becoming pregnant, unless they are using highly effective methods of contraception during dosing and for 3 months following the discontinuation of study treatment. Highly effective contraception methods include:
 - Total abstinence (when this is in line with the preferred and usual lifestyle of the subject). Periodic abstinence (e.g., calendar, ovulation, symptothermal, post-ovulation methods) and withdrawal are not acceptable methods of contraception.
 - Female sterilization (have had surgical bilateral oophorectomy with or without hysterectomy) or tubal ligation at least six weeks before taking study treatment. In case of oophorectomy alone, only when the reproductive status of the woman has been confirmed by follow up hormone level assessment.
 - Male sterilization (at least 6 months prior to screening). For female participants on the study the vasectomized male partner should be the sole partner for that subject.
 - Combination of the following (a+c or b+c):
 - a. Use of oral, injected or implanted hormonal methods of contraception or other forms of hormonal contraception that have comparable efficacy (failure rate <1%), for example hormone vaginal ring or transdermal hormone contraception
 - b. Placement of an intrauterine device (IUD) or intrauterine system (IUS)
 - c. Barrier method of contraception: Condom or Occlusive cap (diaphragm or cervical/vault caps) with spermicidal foam/gel/film/cream/vaginal suppository
15. Sexually active male participants who are unwilling to use a condom during vaginal intercourse while taking the encaleret (study drug) and for 3 months after the last dose of the study drug. Participants should not father a child during active participation in the study starting with the first encaleret dose. Condoms are not required if the subject is vasectomized or if the subject's partner is not a woman of child-bearing potential.
16. Hypersensitivity to any active substance or excipient of encaleret
17. History of drug or alcohol dependency within 12 months preceding the Screening Visit
18. Current participation in other investigational drug studies

19. Unwillingness to refrain from blood donation within 12 weeks prior to admission visit through one year after the last dose of the study drug. If subject donated blood within 12 weeks of the screening visit, they will need to wait until 12 weeks have passed since blood donation for the admission visit.
20. Participants who have a history of diseases of mineral metabolism other than hypoparathyroidism or hyperparathyroidism which investigators believe may impact study endpoints (for example, X-linked hypophosphatemia, rickets, etc).
21. Participants with history of the following :
 - Any cancer except for thyroid cancer, basal cell skin cancer or squamous cell cancer in the last 5 years. Subjects with history of thyroid, basal cell or squamous cell cancers should have received definitive treatment for their malignancies prior to enrollment.
 - Skeletal malignancies
 - Bone metastases
 - Irradiation (radiotherapy) to the skeleton
 - Any other disease that increases the likelihood for osteosarcoma (ex. Paget's disease).
 - Unexplained elevations of alkaline phosphatase

5.3 Inclusion of Vulnerable Participants

5.3.1 Participation of NIH Staff or family members of study team members

NIH staff and family members of study team members may be enrolled in this study as this population meets the study entry criteria. Neither participation nor refusal to participate as a subject in the research will have an effect, either beneficial or adverse, on the participant's employment or position at NIH.

Every effort will be made to protect participant information, but such information may be available in medical records and may be available to authorized users outside of the study team in both an identifiable and unidentifiable manner.

The *NIH Frequently Asked Questions (FAQs) for Staff Who are Considering Participation in NIH Research* will be made available. Please see section [10.1.3](#) for consent of NIH Staff.

5.4 Inclusion of Pregnant Women, fetuses, or neonates

Not applicable

5.5 Lifestyle Considerations

During this study, participants are asked to:

- Consume approximately 1000 mg of daily calcium from their diet, with assistance from a nutritionist.
- Refrain from donating blood at least 12 weeks prior to the admission visit to one year after the last dose of the drug.

- Refrain from eating food from midnight until the next morning during the admission visit

5.6 Screen Failures

Screen failures are defined as participants who consent to participate in the clinical trial but are not subsequently started on treatment. A minimal set of screen failure information is required to ensure transparent reporting of screen failure participants, to meet the Consolidated Standards of Reporting Trials (CONSORT) publishing requirements and to respond to queries from regulatory authorities. Minimal information includes demography, screen failure details, eligibility criteria, and any serious adverse event (SAE).

Individuals who do not meet the criteria for participation in this trial because of failing to meet criteria may be rescreened to reassess the specific criteria that led to screen failure. Only the relevant criteria need to be repeated during rescreening. Rescreened participants should be assigned the same participant number as for the initial screening.

Individuals who meet criteria for participation in this trial but are unable to schedule an admission visit within 180 days of the screening visit, may be rescreened. Rescreened participants should be assigned the same participant number as for the initial screening.

5.7 Strategies for Recruitment and Retention

Hypoparathyroidism has an estimated prevalence of 77,000 adults in North America, with approximately 75% of which are from PSH (Mannstadt et al, 2017). Initial recruitment will include contacting participants with PSH known to NIH investigators. Additional recruitment may proceed through referrals from worldwide clinical and research experts involved in parathyroid surgery and hypoparathyroidism who may be contacted by investigators using a recruitment flier. Finally, outreach through patient advocacy organizations worldwide may also be pursued.

Up to 30 participants may be enrolled to support up to 15 participants entering the treatment phase of the study.

Potential participants will undergo the informed consent process and be screened during an admission or outpatient appointment at the NIH, when they will receive explanation of the clinical trial procedures and requirements. Participants will receive expert clinical oversight of their outpatient therapeutic regimen and management from NIH investigators during the period from screening to the in-house admission and throughout the clinical trial.

Participants will not be billed for any research or related clinical care that participants will receive at the NIH Clinical Center for this study.

5.7.1 Compensation

Participants will be compensated for participation in this clinical trial.

Maximum compensation will be \$885 at the completion of the study with compensation broken down as follows:

Screening visit: \$135

Admission visit: \$720 (\$120 per day x 6 days)

Telephone visits: \$30 (\$10 x 3 telephone visits)

If subject is unable to finish the study, he/she will receive adjusted compensation for part(s) completed also in accordance with NIH HRPP policy 3014-302 Subject Recruitment and Compensation.

Air/train/bus travel will be arranged by the NIH travel agency unless there are extenuating circumstances requiring the subject to book his/her own travel. Miscellaneous out-of-pocket travel expenses (e.g., baggage receipts, airport parking, taxis) will be reimbursed if a receipt is provided. Participants traveling by car from > 50 miles will be reimbursed mileage per NIH policies. Subject copays or co-insurance for local laboratories will be paid or reimbursed if an invoice or receipt is provided.

6 STUDY INTERVENTION

6.1 Study Interventions(s) Administration

6.1.1 Study Intervention Description

The investigational medicinal product (IMP), encaleret, will be provided as film-coated tablets containing the active ingredient encaleret provided in 54 mg dosage strength. Participants will receive encaleret 162 mg (3 tablets) BID per protocol with water.

6.1.2 Dosing and Administration

On Day -1/-2, participants who met eligibility criteria at the screening visit will be admitted to the NIH CC. Participants will not take their magnesium and potassium citrate starting on the morning of Day -2. Participants will not take their standard-of-care calcium or calcitriol starting on the morning of Day -1, and will instead start a personalized calcium supplementation, determined by investigators from their baseline calcium requirements and levels. They will start on a dietary daily calcium intake of approximately 1000 mg per day, which may be adjusted if needed.

Encaleret 162 mg twice a day will be administered to participants on Day 1 to 5. Additional calcium and/or calcitriol will be administered per algorithm (Table D) if required.

Calcium and calcitriol supplementation will be adjusted following the algorithm delineated in Table D with the primary goal of safety. Mild to moderate symptomatic hypocalcemia at any calcium level, cCa < 7 mg/dL, or borderline QT prolongation, would cause investigators to give oral calcium and/or calcitriol. Doses will be determined at the discretion of experienced investigator's understanding of the patient's prior supplement requirements and severity of hypocalcemia. IV calcium may be used for participants with severe hypocalcemic symptoms or QTcF > 500 ms. If a patient develops mild hypercalcemia, then calcium and calcitriol will be held until cCa is less than 9 mg/dL. If cCa has not trended down by 12 hours (or earlier per investigator discretion), encaleret will be stopped. If cCa is > 12 mg/dL, encaleret will be discontinued and calcium and calcitriol will be held until cCa is < 9 mg/dL, when home regimen is restarted.

On Day 3, investigators will add calcitriol supplementation if the albumin-corrected calcium remains < 8.5 mg/dL. The calcitriol dose will be determined by investigators, taking into account the current calcium level and the subject's baseline requirements.

The last dose of encaleret will be given on the night of Day 5. The patient will then resume calcium and calcitriol and be discharged home. If the patient is hypercalcaemic or hypocalcemic, their baseline calcium and calcitriol may be adjusted at discharge. If needed, they may remain at the NIH clinical center until their labs have stabilized to a safe level.

Table D: Titration algorithm:

		Encaleret Titration	Calcium supplementation titration*	Calcitriol titration*	Additional interventions/ monitoring
Hypocalcemia	Severe symptomatic hypocalcemia (seizures, QTcF > 500)**	Continue encaleret	IV calcium until symptoms resolve, transition to oral calcium	Start or increase calcitriol	Monitor blood calcium every 4-6 hours until symptoms resolve
	Mild to moderate symptomatic hypocalcemia OR cCa < 7 mg/dL OR QTcF >480 OR Change in QTcF of >90 from baseline	Continue encaleret	Increase oral calcium and/or start or increase calcitriol		If QT prolonged, repeat ECG twice a day until QTc < 480 or <90 from baseline
	cCa 7-10.2 mg/dL without symptoms of hypo/hypercalcemia	Continue encaleret	Continue calcium	No change in dose until day 3. On day 3, if cCa remains < 8.5 mg/dL, start calcitriol.	
Hypercalcemia	cCa 10.2 – 12 mg/dL	Continue encaleret while holding calcium/calcitriol. Discontinue encaleret if cCa has not trended down up to 12 hours after holding calcium/calcitriol.	Hold calcium until cCa < 9 mg/dL, then restart calcium at a lower dose	Hold calcitriol if taking until cCa < 9 mg/dL, then consider restarting at a lower dose or discontinuing	
	cCa > 12 mg/dL	Discontinue encaleret	Hold calcium until safe to restart home regimen	Hold calcitriol until safe to restart home regimen	IV fluids, consideration of calcitonin therapy if hypercalcemia is prolonged

*This algorithm is meant as a guide and may not have considered all possible scenarios. Calcium and calcitriol titration will be determined by physician investigators specializing in endocrinology and will be based on the prior calcium/calcitriol dosage, the individual patient's prior response, and lab trends. Ultimate decisions regarding calcium and calcitriol changes will be made with the primary goal of patient safety even if this deviates from this algorithm.
 
**Note that severe hypocalcemia and hypercalcemia are not expected to occur during this study. Early intervention and close monitoring is in place to prevent these severe adverse outcomes from occurring.
 
cCa = Albumin-corrected blood calcium, QTcF = QT corrected using the Fridericia's correction equation, IV = intravenous
					

Drug Discontinuation

Encaleret will only be given at the 162 mg BID dosage during this study, but may be discontinued early in the setting of hypercalcemia per the algorithm in Table D.

Participants who develop abnormal clinical or laboratory assessments that indicate continuation of the treatment may put the subject at risk, may have their encaleret dosing interrupted at the discretion of the principal investigator.

Participants who met specific achievement thresholds for both the primary and secondary endpoints may be eligible for early drug discontinuation at the discretion of the principal investigator. The defined thresholds are as follows: The primary endpoint will be considered achieved if the fasting FECa has decreased by >40%. The secondary endpoint will be considered achieved if the participant has achieved concomitant normal or high blood calcium and normal urinary calcium. This approach aims to facilitate the evaluation of the PK-PD relationship (exploratory endpoint) during encaleret withdrawal.

Calcium and calcitriol supplementation and encaleret dose will be adjusted following the algorithm delineated in Table D with the primary goal of safety.

Drug Administration

Encaleret will be dispensed by the NIH Pharmacy. It will be provided as film-coated tablets containing the active ingredient encaleret provided in 54 mg dosage strength. Participants will receive encaleret 162 mg (3 tablets) every 12 hours per protocol with water.

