A thorough QT study in healthy subjects showed no clinically meaningful QTc prolongation following a single oral dose of up to 100 mg encaleret at any of the examined timepoints. In patients with ADH1, who are hypocalcemic at baseline, QTc decreased towards normal on encaleret, in parallel with normalization of calcium and magnesium level. Of note, although pre-encaleret cCa levels in this population ranged from 6.4 to 9 mg/dL, no subjects had QTcF or QTcB interval >480 msec.

In preclinical safety and toxicology studies, the dose-limiting effects of encaleret were related to mechanism-based elevations in serum calcium concentrations and effects on calcium

homeostasis. In contrast, no off-target or other tissue or organ-specific toxicities were identified.

The metabolism and elimination of encaleret in preclinical studies has been conducted. Based on non-clinical data, fecal excretion was the main route of elimination. In humans, excretion of unchanged encaleret and metabolites into urine was minimal (< 5% as total of parent and metabolite). The two major glucuronide metabolites (M1, M3) showed similar pharmacokinetics as the parent drug, with M1 median t_{max} ~2 hr. and M3 median t_{max} ~1.5 hr. For M1 (inactive), concentrations in plasma were approximately 2-fold higher than those of parent drug; M3 (active) concentrations were low (10% compared to parent). Neither M1 nor M3 showed prolonged elimination (see Investigator Brochure for details). Encaleret has not been formally studied in patients with severe to moderate renal impairment but significant dose adjustments in this population are not expected given elimination pathway and in the setting of the protocol dose escalation safety review process.

In a human drug interaction study, encaleret co-administration with ketoconazole, a potent CYP3A4 inhibitor, resulted in ~1.67x increase in C_{max} and ~2x increase in AUC₀₋₂₄ with slightly less effect on M1 and M3.

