Day -2 or Day -1 (Admission): Participants will be admitted to the NIH CC either the day prior to dosing or two days prior to dosing based on subject convenience. All participants will be instructed to stop taking calcitriol and home calcium dosage, with last doses on Day -2. Participants on magnesium or potassium citrate will be instructed to stop these supplements, with last doses on Day -3. Calcium supplementation with calcium carbonate(500 mg elemental calcium) three times a day will start on Day -1. Baseline 24-hour urine will be opened the morning of Day -1, and fasting laboratory assessment will be obtained. Attempts will be made to collect fasting calcium levels prior to the morning calcium dosage, however, calcium will be given to participants if clinically indicated (for example, in the setting of hypocalcemia).

Days 1 to 5: Encaleret 162 mg BID will be taken orally by the patient. Detailed summary of planned calcium and calcitriol therapy is presented in Figure 2 and a dosing algorithm is presented in Table D. Frequent blood and urine sampling for 24-hours will be performed for safety and outcome measures (see [Table A and Table B](#)). Encaleret will be administered in the morning and evening with water approximately 12 hours between each dose. The last dose of study medication will occur on the evening of Day 5. Daily ECG will be performed for monitoring of QT interval.

Day 6 (Discharge): After the blood sampling is collected on the morning of Day 6 and the 24-hour urine is closed, all participants will resume their prior conventional treatment regimen. During Day 6, cCa levels will be monitored until the patient is discharged. This admission can be extended if additional monitoring or treatment (e.g., to stabilize calcium) is needed prior to discharge.

Follow-up:

Outpatient testing done on day 8-12 (Less than 7 days after expected discharge from the NIH clinical center) will be collected either at the NIH CC or local laboratory. Blood samples collected will be evaluated for blood creatinine, albumin, calcium, magnesium, phosphate, and PTH. A telephone contact to the patient will be conducted once calcium results are available to be reviewed with investigative team. Additional outpatient testing to follow up safety issues will be performed as needed.

An additional two telephone contacts will be performed at 30-days (\pm 7 days) and 90-days (\pm 7 days) after the last encaleret dose for screening of AEs and pregnancies, respectively.

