Appropriate evaluations may include serial cCa measures, initial, daily, and follow-up ECG as appropriate based on clinical assessment (bradycardia e.g.) and/or if cCa is persistently < 7 mg/dL.

Graded interventions according to the expert judgment of the NIH investigators will include standard measures such as oral calcium and/or calcitriol supplementation (see Table D) for mild-moderate events. In the case of unresolving or worsening hypocalcemia with more acute clinical manifestations including worsening neurocognitive deficits, seizures, tetany, hypotension, or cardiac dysfunction, for example, appropriate urgent intervention, also according with standards of care, will be undertaken by the site, including administration of intravenous calcium gluconate (See Table D).

Osteosarcoma as an Adverse Event of Special Interest:

The risk to participants in this study for developing osteosarcoma is very low. However, because a carcinogenicity study suggested high-dose, long-term encaleret increased the risk of

osteosarcoma in rats with intact parathyroid glands, we will also record any development of osteosarcoma in our participants as an adverse event of special interest.

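### Table D's rule for ending repeat ECGs joins its two QTc limits with 'or', so as written it can already be met when only one QTc trigger has been crossed

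*Combined protocol and SAP*

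**What the plan says.** The relevant text is the mild-to-moderate row of Table D in section 6.1.2. Besides symptoms or a corrected calcium below 7 mg/dL, the row is entered on "QTcF >480 OR Change in QTcF of >90 from baseline". Either limit alone is enough. The row's monitoring cell applies when the QT is prolonged and tells staff to "repeat ECG twice a day until QTc < 480 or <90 from baseline".

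These other places bear on the rule:

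- **Upper edge of the row.** The row above it begins at "Severe symptomatic hypocalcemia (seizures, QTcF > 500", so the QTcF range at issue runs up to 500 ms.
- **Baseline.** Section 5.2, item 9: "Participants with screening QTcF (using the Frederica equation) > 450 milliseconds (ms) will not be eligible for the treatment phase".
- **Background ECGs.** Section 8.2, for Days 1 to 5: "Daily ECG will be performed for monitoring of QT interval". Table A schedules ECGs at screening and on Days -1 to 5, with none on Day 6.
- **Discretionary ECGs.** Section 8.3.9 allows "initial, daily, and follow-up ECG as appropriate based on clinical assessment".
- **Prior experience.** Section 2.3.1 reports that in ADH1 "no subjects had QTcF or QTcB interval >480 msec".

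No other section restates the release rule or says that both limits must be cleared.

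**The concern.** A release rule should be the negation of the trigger that it ends. The trigger is an 'or' of two limits, so its negation is an 'and'. The document uses 'or' in both places. Two consequences follow from the wording:

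1. A participant who crosses only one limit is, by definition, still inside the other, so the repeat ECGs can end before they start.
2. A participant who crosses both can be released as soon as one clears, with the other still exceeded.

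The trigger also names QTcF, while the release says only QTc. Section 2.3.1 mentions both QTcF and QTcB, so the correction formula should be named in both places.

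This is the row's only QT-specific monitoring instruction. Section 4.3 accepts that these patients may be at greater risk of symptomatic hypocalcemia. The next step up, QTcF above 500 ms, leads to IV calcium (6.1.2) and is among the events that pause recruitment for DSMC review (10.2). The band just below 500 ms is where the step-up from daily to twice-daily ECGs is meant to apply.

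**Working it through.** **Inputs.** Trigger and release limits of 480 and 90 (Table D; the row gives no units, read here as ms). Upper edge of 500 ms (Table D, severe row). Screening QTcF of at most 450 ms (5.2, item 9). The documents give no distribution of baseline or on-treatment QTcF in PSH, so baselines are assumed and the result is shown across a range.

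**Rules.** Let *b* be baseline QTcF and *q* a later QTcF, in whole ms, with *q* ≤ 500.

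- Trigger T: *q* > 480 or *q* − *b* > 90
- Release as written, R: *q* < 480 or *q* − *b* < 90
- Exact negation of T: *q* ≤ 480 and *q* − *b* ≤ 90

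**Step 1: single values.**

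- *b* = 420, *q* = 485: 485 > 480, so T is met. The rise is 485 − 420 = 65 < 90, so R is met at once.
- *b* = 380, *q* = 475: the rise is 475 − 380 = 95 > 90, so T is met. But 475 < 480, so R is met at once.
- *b* = 400, *q* = 495: the rise is 95, both limits are crossed and R is not met. If *q* falls to 485, the rise is 85 < 90, so R is met while QTcF is still above 480.

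**Step 2: how much of the trigger range is affected.** For each assumed baseline, count the values that meet T, and those that meet T and R together.

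| Assumed baseline (ms) | Values meeting T | Of these, R already met |
|---|---|---|
| 360 | 451–500: 50 | 451–479: 29 |
| 370 | 461–500: 40 | 461–479: 19 |
| 380 | 471–500: 30 | 471–479: 9 |
| 390 | 481–500: 20 | 0 |
| 400 | 481–500: 20 | 481–489: 9 |
| 410 | 481–500: 20 | 481–499: 19 |
| 420, 430, 440, 450 | 481–500: 20 | 481–500: 20 |

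At 420 and above, a rise of 90 would need *q* ≥ 510, which is outside the row. The change limit is therefore never reached, and the release is met at every triggering value.

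**Step 3: is this general?** Take every whole-ms baseline from 350 (an assumed floor) to 450, and every *q* from *b* to 500.

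- Exactly one limit crossed: 1830 combinations. R is already met in 1770. The other 60 are exact ties (*q* = 480 or a rise of exactly 90).
- Both limits crossed: 1010 combinations. R is met in none of them at entry.

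**Step 4: the corrected release.** The exact negation of T cannot overlap T. The overlap is 0 at every baseline in the table.

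**The case against.** The strongest reply is that no clinician would read the rule this way. The word 'until' presupposes that the condition is not yet met, and the two release limits mirror the two triggers in order. The natural reading is that each limit clears its own trigger. That is probably the intent, but it is not written, and it does not settle what happens to someone who crossed both. Reading 'until' as requiring at least one repeat does not cure it either: with baseline 420 and QTcF 485, a repeat of 495 (rise 75) still ends the series.

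The second reply is that release does not mean unmonitored, and this largely stands. Daily ECGs continue through Day 5, investigators review each one, and blood is drawn several times a day. Any later value above a limit meets the row again and brings the calcium or calcitriol response. Section 8.2 allows the admission to be extended. These limit the harm but do not correct the rule. After a Day 5 trigger, the remaining provisions are discretionary and the extension clause does not name ECGs.

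Third, Table D's footnote calls the algorithm a guide. The asterisk, however, sits on the calcium and calcitriol columns, and the permission to deviate concerns changes to those two. It does not tell staff how to read the ECG instruction.

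Fourth, the counts above are integers on assumed baselines, not probabilities or participants. That is correct. They show which readings the rule fails for, and should not be quoted as a rate.

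Finally, QTcF is the only correction defined in Table D, so QTc may be shorthand. Naming it costs nothing.

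**Conclusion.** The rule is wrong as written, with small practical impact. The logical result depends on no assumption about baseline: crossing exactly one limit satisfies the release at once, except at exact ties. How much of the row is affected does depend on baseline, from none of the triggering values at 390 ms to all of them at 420 to 450 ms.

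The loss is confined to the mandated second daily ECG and any mandated repeat after a Day 5 trigger. Scheduled ECGs on Days -1 to 5, discretionary follow-up and the row's calcium and calcitriol response are unaffected. So are the dose, the endpoints, the sample size and the power. The number of participants concerned is unknown and may be zero among up to 15 treated. No ADH1 subject exceeded 480 ms, although that is a different population. Because it is a stated safety instruction that gives the wrong result if followed literally, it should be corrected.

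**What to change.** In the monitoring cell of Table D's mild-to-moderate row, replace the release with: *repeat ECG twice a day until QTcF is no longer >480 ms AND the change in QTcF is no longer >90 ms from baseline*. State QTcF and ms in both the trigger and the release.

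This keeps the existing thresholds and is the exact negation of the trigger. No value can meet both, and the ties at 480 and 90 are resolved. Changing only 'or' to 'and' while keeping the strict limits would also remove the main fault, but would leave a value of exactly 480, or a rise of exactly 90, outside both trigger and release.

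The cost is a one-line edit and at most a few extra ECGs in inpatients who already have one each day.
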